1.1 BACKGROUND

Type 1 diabetes (T1D) is a disease characterized by progressive β -cell loss with eventual dependence on exogenous insulin. The incidence of T1D is rising at a rate of nearly 3% per year, and the disease contributes over \$14.4 billion annually to U.S. healthcare expenditures [1, 2]. While immunomodulatory therapy administered near the time of clinical diagnosis has shown some efficacy in attenuating T1D progression, the long-term effectiveness of these drugs has been negligible [3-7]. Given these failures, there is a critical need for a simple, tolerable, cost-effective method to mitigate the disease process and burden associated with daily diabetes management.

Compared to healthy individuals, people with both type 1 and type 2 diabetes demonstrate gut dysbiosis (microbial imbalance) with a higher gram-negative to gram-positive gut bacterial ratio (creating a pro-inflammatory milieu) and fewer bifidobacteria, an important microbial population associated with many health benefits [8-13]. Further, the gut microbiome composition of T1D children shows increased virulence factors, phage, prophage, motility genes and higher response to stress [14-18], in addition to a lower count of bacteria producing butyrate, a short chain fatty acid (SCFA) with anti-inflammatory actions [19].

The effect of gut microbiome modulation on glycemia has been assessed using both prebiotics (supplements containing substrates for the microbiota) and probiotics (supplements containing microbiota). Animal studies have shown that pre and probiotic use can change the gut microbiome profile, modulate the immune system, and improve glucose tolerance [20-22]. In persons with type 2 diabetes (T2D), prebiotics improve hemoglobin A1c (HbA1c) and postprandial glycemic excursion as well as reduce insulin resistance [23-26]. Thus, it appears that altering the gut microbiome may improve glycemia and improve insulin sensitivity.

A novel approach to mitigating T1D is perturbation of the gut microbiome using high-amylose maize starch (HAMS), a well-tolerated source of dietary fiber with selective fermentation properties. HAMS consumption shifts the gut microbiome profile towards SCFA fermenters. Further, HAMS that is acetylated and butyrylated (HAMS-AB) releases large amounts of beneficial SCFAs after colonic bacterial fermentation. Indeed, recent T1D mouse studies [22] have shown that HAMS-AB feeding shifted the gut microbiome profile towards fermenters, resulting in higher blood and fecal concentrations of the microbial metabolites acetate and butyrate (both beneficial SCFAs). These changes were associated with lower rates of progression to T1D, lower circulating inflammatory marker concentrations, and less islet autoimmunity. Data to date using HAMS in humans are more limited. When given to non-diabetic adults, HAMS lowers post-prandial glucose production and improves insulin sensitivity [27, 28].

1.2 Overview

Given these promising findings in animal models of T1D as well as adult non-diabetic studies, we hypothesize that HAMS-AB will alter the gut microbiome profile in humans with T1D and increase SCFA production and that these changes will be associated with improved β -cell function, overall glycemia, and β -cell health (as measured by markers of β -cell stress and death). We plan to perform a pilot, randomized, controlled cross-over trial of HAMS-AB in 12 individuals with recently diagnosed T1D to determine HAMS-AB effects on the gut microbiome profile, SCFA production, glycemia, markers of β -cell function, stress, and death.

This pilot study is a single center trial. Twelve newly diagnosed T1D youths with a BMI<85% and within 4-36 months of diagnosis who have measurable endogenous insulin production, assessed using serum C-peptide, and are, therefore, in the honeymoon period, will be recruited. We have chosen this cohort since the microbiome profile differs by age [29] and BMI [30], and the progression of T1D differs between children and adults [31]. Additionally, there is ample published experience studying healthy adolescents and their microbiome changes with corn fiber supplementation [32, 33], and therefore, we have chosen to pilot this intervention in a similar age group with known published data. In addition, to assess changes more accurately in β -cell function, we will include those in the honeymoon period as there is sufficient measurable C-peptide secretion during this time. The honeymoon period is the time shortly after T1D diagnosis when the β -cells undergo partial and temporary recovery and produce enough insulin to reduce insulin needs and aid with glycemic control [34, 35].

The **objectives** of this study are to assess the HAMS-AB effects on the gut microbiome profile, SCFA production, glycemia and β -cell health and function in humans with T1D. We **hypothesize** that HAMS-AB will (i) improve the gut microbiome profile in humans with T1D, (ii) increase SCFA production, and (iii) improve β -cell function, β -cell health and overall glycemia. We propose the following Specific Aims:

AIM 1: Determine the effect of HAMS-AB on the gut microbiome profile and SCFA production in children with recently diagnosed T1D. We *hypothesize* that HAMS-AB consumption will shift the gut microbiome to microbial populations that are capable of HAMS-AB fermentation and increase SCFA production. Twelve youths (11-17 years old) will consume HAMS-AB or follow the standard of care recommended diabetic diet daily for [49,50] 4 weeks and then cross over after a 4-week washout period. DNA will be extracted from fecal samples obtained followed by 16S RNA sequencing for gut microbial community analysis at baseline and at each visit during the study period [32, 33]. SCFAs will be analyzed using standard methods [36, 37].

AIM 2: Determine the effect of HAMS-AB on glycemia and β -cell function and health. We *hypothesize* that the prebiotic HAMS-AB will improve overall glycemia including reducing glycemic variability in recently diagnosed persons with T1D. We will compare glycemic/ β -cell measures pre/post intervention with HAMS-AB and between the intervention and control groups. We will measure glycemia using HbA1c, average glucose and glucose variability using continuous glucose monitoring (CGM) [38-40]. We expect to see an improvement in glycemia in response to HAMS-AB intake. We will assess β -cell function using mixed meal tolerance (MMTT)-derived C-peptide measures. We *expect* that measures of β -cell stress/death will show improvement following the use of HAMS-AB. We will determine β -cell stress using proinsulin/C-peptide (PI:C) ratios [41]. We will assess β -cell death by differential methylation of proinsulin (INS) DNA [42].

Upon successful completion of this pilot study, we expect to assess the effect of prebiotic administration on the gut microbiome profile, SCFA production, glycemia and β -cell function in humans with T1D. The knowledge generated by the proposed research will provide critical experimental information needed to substantiate a fully powered study.

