3.1 STUDY DESCRIPTION

This study will be a single center, controlled, randomized trial in young individuals newly diagnosed with type 1 diabetes. We are enrolling youth with new onset T1D with documented continued residual C-peptide production. Within 30 days of screening during which eligibility will be determined, subjects will have a 4-week treatment period with HAMS-AB or will be provided with guidelines on the generally recommended diabetic diet for youths with T1D [49, 50]. After a 4-week wash-out period the durability of effect will be assessed in those who received the prebiotic and during this washout period, both the study and control arm will be permitted to consume a regular diet. This design has been used in other studies of prebiotic administration with a 3–4-week intervention period and a 3–4-week washout phase [21, 32, 33]. Subjects will then cross over to either HAMS-AB or diet control for another 4 weeks.

A full dosing description can be found in section 6.2.

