6.1 STUDY DESIGN

6.2 RANDOM ASSIGNMENT

Subjects will be randomly assigned (6 in each arm) to either HAMS-AB plus a recommended diabetic diet or control diabetic diet alone [49, 50] for the first 4 week of treatment period. After a suitable washout period during which participants do not need to follow the recommended diet or use the supplement, subjects will continue for 4 weeks after a cross-over. All participants will be expected to follow the guidelines for a healthy diabetic diet during the study period, except for during the 4-week washout period.

A computer-based randomization plan will be prepared by the principal investigator. The document will be kept by the study team for use. As a subject is screened and qualifies, he/she will be assigned in order of screening date on the computer-generated document. One master list will be maintained in a confidential central shared folder for use. Subjects will be replaced on an ongoing list if they drop out.

Participants will be instructed to consume HAMS-AB with food, such as apple sauce or oatmeal, in two divided doses at breakfast and dinner at a total daily dose to be calculated as has been previously described for children: 10g plus 1g per year of age daily [44]. The prebiotic will be dispensed by the Investigational Drug Services (IDS) at Indiana University.

HAMS-AB will be in the form of acetylated and butyrylated **HYLON® VII** corn starch.

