6.3 SCHEDULE OF EVENTS

Study Phase	Screening	Baseline- Intervention	Washout	Crossover- Intervention	Follow-Up	Early Termination Visit
Visit Number	1	2	3	4	5	
Visit Window		≤30 days after Visit 1	+/- 3 days 28 days after Visit 2	+/- 3 days 28 days after Visit 3	+/- 3 days 28 days after Visit 4	
Informed consent/Accent	X					
Inclusion/Exclusion criteria	X					
Historical Data/Demographics*	X					
Pancreatic Autoantibodies †	X					
Random C-peptide concentration††	X					
Randomization		X				
Pregnancy test**	X	X	X	X	X	X
Current Medical data***		X	X	X	X	X
Pubertal Tanner staging with physical exam	X					
Ht/Wt measurement and vitals	X	X	X	X	X	X
Supervised CGM insertion (and training, if applicable on use) †††		X		X		
C-peptide by 2-hr MMTT††††			X		X	X
HbA1c		X			X	X
Blood samples for biomarkers (PI:C and INS DNA)		X	X	X	X	X
Provision of HAMS-AB		X		X		
CGM download			X		X	X
Stool samples****		X	X	X	X	X
Whole blood for additional T1D testing		X	X	X	X	X
Serum and plasma for storage^		X	X	X	X	X
Adverse event assessment*****		X	X	X	X	X
Dietary Assessments*****		X	X	X	X	X
Verbal Diet recall	X					
Sampling of prebiotic	X					

Data Collection:

***Historical data:** Date of birth, sex, Race/Ethnicity, date of diagnosis of T1D.

**To be done in girls of reproductive potential.

*****Current Medical Data (All visits except screening):** Medication use including types of insulin, means of insulin administration, and total daily insulin dose (u/kg body weight, averaged over the 3 days prior to each study visit), use of other medications.

******Stool samples** will be collected at home using a kit (Zymo feces catcher and RNA/DNA shield fecal collection tubes) within 3 days of presentation to each visit.

*****Participants will be assessed for **safety** with questions regarding general well-being as well as specific questions to evaluate for adverse events. Participants will also be questioned about stool form and frequency, gastrointestinal symptoms, fevers, or infection.

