*******Dietary Assessments** will be ideally obtained using the Automated Self-Administered 24-Hour (ASA24) dietary assessment tool [46-48], a web-based tool for administering automatically coded, self-administered recalls/food records. This will allow assessment of dietary fiber intake along with other dietary components. Participants will be asked to fill these in for the 24 hrs. diet recall prior to each stool collection in a time frame of +/- 3 days from the stool sample collection. This can also be completed during the study visit. Diet diaries will be accepted in lieu of the online questionnaire. Participants will be asked to record all meals and snacks, time of day, number of servings, major food components or description (for example chicken or protein), estimated portion sizes and whether they completed the meal or not, and any drinks including water.

†Pancreatic autoantibodies to be tested only in those with no evidence of being tested for antibodies in their medical chart to confirm T1D.

††Random, non-fasting c-peptide: C-peptide level will be analyzed at Indiana University Translation Core Lab using a two site immuno-enzymometric assay using a Tosoh 2000 auto-analyzer (TOSOH, Biosciences, Inc., South San Francisco, CA). The C-peptide assay is calibrated against the WHO IS 84/510 standard and has a sensitivity level of 0.05 ng/mL.

†††At visit 2 (baseline/intervention) and 4 (crossover), a blinded CGM sensor will be inserted in those participants who are not currently using a CGM as part of their routine care. Training will be provided on calibration of the sensor, its use in blinded mode, and sensor insertion. Participants will be reminded to insert a sensor at home after approximately 14 days and continue using the blinded sensor for an additional 14 days. Participants will use their own home blood glucose meter or (if had been previously using one) CGM for regular blood glucose monitoring. The participant will return after 4 weeks to assess the CGM data. CGM must be used for at least 200 hours (equivalent to 8.3 days out of 14 days)

††††C-peptide by 2-h MMTT: 2-hour MMTT will be performed using the standardized protocol utilized by the TrialNet Centers [51]. The early discontinuation MMTT will only be done if it has been at least 6 weeks since the last MMTT.

^Serum and Plasma for storage – subject has option to consent or deny storage. Will be used for future type 1 diabetes research assays.

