6.4 STUDY VISITS

Visit 1 – Screening

This visit will be at the hospital or research center. It will last approximately 1-2 hours and will include:

- Obtain informed consent/assent documents and determine inclusion and exclusion criteria
- Measurement of height and weight to determine BMI percentile eligibility and physical exam including pubertal staging
- Obtaining Vital signs (heart rate, temperature, blood pressure, and respiratory rate)
- Obtaining medical history
- Dietary assessment by verbal recall
- Obtaining blood sample (approximately 1.5 tablespoon) – Random non-fasting c-peptide, pancreatic autoantibodies if not previously done to confirm T1D diagnosis
- For female adolescents: urine will be collected for a pregnancytest
- Subject to sample prebiotic for palatability to ensure compliance

Visit 2 – Baseline-Intervention

This visit will be at the hospital or research center. It will last approximately 1-2 hours and will include:

- Measurement of weight and bedside nurse assessment such as general appearance, respiratory and cardiac assessment.
- Obtain vital signs (heart rate, temperature, blood pressure, and respiratory rate)
- Collecting a diet history (diary or questionnaire)
- Collecting Adverse Events (if applicable)
- Obtaining medical history and insulin use

Obtaining blood samples (approximately 2 tablespoons) – HbA1c, Serum biomarkers of beta cell stress and death (PI:C and INS DNA), other T1D testing, and serum and plasma for storage.

- Some of the blood will be stored for future T1D research use

- CGM placement and training for participants not currently using one.
- For female adolescents: urine will be collected for a pregnancytest
- Collecting stool samples prior to or the morning of the visit (a stool collection kit will be shipped to the participants once eligibility is confirmed)
- Study Randomization to either supplement or standard of care diabetes management and a diabetic diet.
– Supplement (HAMS-AB) will be provided and will be taken by mouth twice daily with food such as apple sauce or oatmeal as described in Section 6.2. Instructions will be provided for recommendations on a healthy diabetic diet.
- A new stool collection kit will be provided for the next visit

Visit 3 - Washout

This visit will be at the hospital or research center. It will last approximately 2-4 hours and will include:

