8.0 STATISTICAL CONSIDERATIONS

A sample size of 12 with a cross over design (i.e., 12 per arm) is considered adequate to estimate effect sizes for efficacy to aid in designing future trials for responses that are normally distributed [52]. Simple comparisons will be performed using chi-square for categorical variables and t-tests for continuous variables. Random attritions and failed screens will be replaced. An intention to treat analysis will not be appropriate given the crossover design. Adverse events will be presented as the proportion of each event seen. This is considered a minimal risk study with low risk for minor adverse events such as mild gastrointestinal symptoms that could be related to increased dietary fiber intake. Our primary outcome is changes in the gut microbiome profile. To determine the diversity and richness of the microbiome, we will calculate a diversity index for both the pre- and post-intervention time points for each recipient. Microbial sequence analysis and statistics will be analyzed using the Quantitative Insights into Microbial Ecology (QIIME) 1.8.0 software as previously described [53].

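### HbA1c is drawn only at Visits 2 and 5, so no completer has it at both ends of the HAMS-AB period, and HAMS-AB v control is left as 6 v 6 rather than 12 per arm

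*Combined protocol and SAP*

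**What the plan says.** Aim 2 in section 1.2 states the measures: "We will measure glycemia using HbA1c, average glucose and glucose variability using continuous glucose monitoring (CGM"). It says the glycemic and β-cell measures will be compared "pre/post intervention with HAMS-AB and between the intervention and control groups".

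The design is a two-period crossover with six participants per sequence (6.2). Each treatment period lasts 4 weeks, with a 4-week washout between them. Period 1 runs from Visit 2 to Visit 3 and period 2 from Visit 4 to Visit 5.

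In the schedule of events (6.3), the HbA1c row is marked at Visit 2, Visit 5 and the early termination visit only. The visit lists in 6.4 agree. The Visit 2 draw is "HbA1c, Serum biomarkers of beta cell stress and death (PI:C and INS DNA), other T1D testing, and serum and plasma for storage", and the Visit 5 list also names HbA1c. The lists for Visits 3 and 4 name PI:C, INS DNA, other T1D testing and stored samples, but not HbA1c. The undefined T1D testing is listed separately from HbA1c at Visits 2 and 5, so it cannot be read as covering it.

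Section 8.0 gives the basis for the sample size: "A sample size of 12 with a cross over design (i.e., 12 per arm) is considered adequate to estimate effect sizes". It names t-tests for continuous variables and states no crossover model.

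**The concern.** A crossover earns its precision by observing each participant under both conditions. For a pre/post comparison it also needs a value at each end of the treatment period. HbA1c has neither. The two draws sit at the outer edges of the 12 weeks, and the two inner visits, where one condition ends and the next begins, have none.

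The purpose of the pilot is to supply effect sizes for a later, fully powered study (1.2 and 8.0). A reader of Aim 2 and section 8.0 would expect an HbA1c effect estimated from 12 participants under each condition. The schedule cannot supply that. Because the table and the visit text agree, this is a feature of the plan and not a typographical slip in one place.

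**Working it through.** **Inputs.** Six participants per sequence (6.2); 12 completers, since recruitment stops once 12 have finished the 12-week visit (3.3); visits nominally at days 0, 28, 56 and 84, each window ±3 days (6.3); HbA1c at Visits 2 and 5 (6.3, 6.4).

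**Step 1: the plan's own figure.** A measure taken at all of Visits 2 to 5, such as stool, has an end-of-HAMS-AB value in 6 participants at Visit 3 and 6 at Visit 5. That is 6 + 6 = 12, and likewise 12 for control. This reproduces the 12 per arm of section 8.0. It is a count only: the section gives no SD, effect size, alpha or power.

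**Step 2: the same count for HbA1c.**

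| Sequence (n) | HAMS-AB period | HbA1c at its start | HbA1c at its end | HbA1c at end of control |
|---|---|---|---|---|
| HAMS-AB first (6) | Visit 2 to 3 | yes (Visit 2) | no (Visit 3) | yes (Visit 5) |
| Control first (6) | Visit 4 to 5 | no (Visit 4) | yes (Visit 5) | no (Visit 3) |

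- Both ends of the HAMS-AB period: 0 + 0 = 0 of 12.
- End of both conditions: 0 + 0 = 0 of 12.
- End-of-condition values: 6 for HAMS-AB and 6 for control, in different people.

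**Step 3: what the Visit 2 to Visit 5 change contains.** In both sequences it spans 28 + 28 + 28 = 84 days of HAMS-AB, washout and control diet; only the order differs. Let p be the 12-week change that would occur without HAMS-AB, e the HAMS-AB effect on HbA1c present when a HAMS-AB period has just ended, and c the part still present in the HAMS-AB-first group at Visit 5.

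- Expected change, control first: p + e.
- Expected change, HAMS-AB first: p + c.
- Pooled over the 12: p + (e + c)/2. This cannot be separated from p.
- Difference between sequences: e − c. This equals the HAMS-AB effect only if c = 0, that is, if there is no carryover.

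The second contrast is the 6 v 6 comparison at Visit 5, with or without adjustment for Visit 2.

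**Step 4: the counts after adding draws.**

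| HbA1c visits | Both ends of HAMS-AB | End of both conditions |
|---|---|---|
| 2, 5 (as planned) | 0 of 12 | 0 of 12 |
| 2, 3, 5 | 6 of 12 | 12 of 12 |
| 2, 4, 5 | 6 of 12 | 0 of 12 |
| 2, 3, 4, 5 | 12 of 12 | 12 of 12 |

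**Step 5: two possible contrasts once all four visits exist.** Assume a common variance σ² and an equal correlation ρ between any two visits; the documents give neither value.

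- End of period (Visit 3 v Visit 5): each within-participant difference has variance 2(1 − ρ)σ². Averaging the two sequences of six gives ¼ × 2 × 2(1 − ρ)σ²/6 = (1 − ρ)σ²/6.
- Period change (Visit 3 minus 2 v Visit 5 minus 4): each difference has variance 4(1 − ρ)σ², giving ¼ × 2 × 4(1 − ρ)σ²/6 = (1 − ρ)σ²/3.

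The ratio is 2 at any ρ below 1. The choice therefore matters and should be made before the data are seen.

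**The case against.** The strongest reply is that the plan never promised a within-participant HbA1c analysis. Aim 2 speaks of intervention and control groups, section 8.0 plans t-tests, and at Visit 5 six participants have just finished HAMS-AB and six have just finished control. That contrast fits the wording. This stands, and so a reader who infers that no HbA1c comparison at all is possible goes too far. The reply does not rescue the pre/post comparison, and 6 v 6 is not 12 per arm.

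It may also be said that CGM carries the glycemia outcome and that section 3.4 already concedes low power. CGM is placed at Visits 2 and 4 and downloaded at Visits 3 and 5, so both conditions are covered. A reader might infer that Aim 2's glycemia comparison fails as a whole; the documents do not support that. The caveat in 3.4, however, rests on variability and small numbers. It does not disclose that the time points are absent.

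A third reply is that HbA1c moves too slowly for 4-week periods to be informative. That may be the reason for the sparse schedule, but the documents do not give it. If it is the reason, Aim 2 should not promise the comparison.

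A reader might also infer a broken promise on durability, because 3.1 says "After a 4-week wash-out period the durability of effect will be assessed in those who received the prebiotic". That sentence names no measure, and stool, PI:C and INS DNA are sampled at Visit 4. It does not commit the plan to HbA1c at the end of washout.

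Finally, the early termination draw could give an on-treatment HbA1c in someone who stops during a first HAMS-AB period. Such a person is not one of the 12 completers, so the counts are unchanged.

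**Conclusion.** The point holds and should be fixed. For HbA1c, the pre/post HAMS-AB comparison in Aim 2 cannot be made over the HAMS-AB period in any of the 12 completers. HAMS-AB v control cannot be made within participant in any of them either. A between-group comparison survives only as 6 v 6 at Visit 5, and reading it as a HAMS-AB effect requires no carryover in the HAMS-AB-first six.

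The counts come straight from the schedule and need no assumption beyond six completers per sequence. The twofold variance ratio rests on equal variances and equal correlation between visits. How fast HbA1c responds and how far it carries over are not given in the documents, so no figure is put on either.

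The weight is modest. The endpoint text in 3.4 lists glycemia as a secondary outcome without naming HbA1c, which appears as one of several Aim 2 measures. The primary microbiome outcome, sampled at Visits 2 to 5, is untouched.

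**What to change.** Add HbA1c at Visits 3 and 4 in 6.3 and 6.4. Both are needed: Step 4 shows that neither alone restores both comparisons. Analyse HAMS-AB v control within participant with a period term. State in advance whether the main contrast is end of period (Visit 3 v Visit 5) or period change (Visit 3 minus 2 v Visit 5 minus 4), noting the variance cost of the latter. Label the result supportive, because HbA1c may respond only in part over 4 weeks and may carry over a 4-week washout.

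The cost is about 12 × 2 = 24 assays, a schedule amendment and a short addition to section 8.0. Blood is already drawn at both visits, so no extra visit or needle stick is needed. The stated volumes at Visits 3 and 4 (about 5 and 2 tablespoons) match those at Visits 5 and 2, which already include HbA1c.

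If HbA1c is not added, amend Aim 2 to say that HbA1c is descriptive and will not serve as a pre/post or within-participant treatment comparison. That costs wording only.
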